8.2.9 Echocardiogram

An echocardiogram will be taken at screening.

Left ventricular ejection fraction will be summarized using descriptive statistics.

The echocardiogram will be categorised as ‘normal’/ ‘abnormal, not clinically significant’/ ‘abnormal, clinically significant’. The number (%) of subjects with evaluations falling into each category will be summarized.

8.2.10 Chest X-ray and Computed Tomography (CT) Scan

A chest x-ray will be taken at screening, in addition a CT scan will be performed if the x-ray shows evidence of severe lung disease.

Both the chest x-ray and the CT scan will be categorised as ‘normal’/ ‘abnormal, not clinically significant’/ ‘abnormal, clinically significant’. The number (%) of subjects with evaluations falling into each category will be summarized.

8.2.11 Skin Lesions

The number (%) of subjects with any suspicious skin lesions at screening, having a biopsy and falling into each category of result (‘normal’/ ‘abnormal, not clinically significant’/ ‘abnormal, clinically significant’) will be summarized.

8.2.12 Bone Marrow Harvest

The number (%) of subjects with each blood type, having a transfusion of PRBC and with each reason for a lack of back-up stem cells (if appropriate) will be summarized. If there is a repeated harvest, these data will be summarized for each evaluation.

Total number of nucleated cells and total CD34+ cell count in the bone marrow harvest will be summarized using descriptive statistics along with the number of mononuclear and total nucleated cells stored for back-up.

8.2.13 Busulfan Administration

For each administration of Busulfan, the duration of administration, dose given and AUC will be summarized using descriptive statistics. In addition, for Day -4/-3, the calculated Busulfan dose for Day -2/-1 will be summarized.

8.2.14 Busulfan Pharmacokinetics

For each administration of Busulfan, the PK parameters (C_{max} , T_{max} , AUC_{0-t} , AUC_{0-13} , $AUC_{0-\infty}$) will be summarized using descriptive statistics.

8.2.15 OTL-101 Administration

The number (%) of subjects who received OTL-101 will be summarized along with any reasons for non-administration.

The number (%) of subjects who were pre-medicated with acetaminophen or diphenhydramine will be summarized.

For each bag of product, the volume, number of CD34+ cells and the planned volume to be infused, the duration of infusion, the volume administered and the % cell viability will be summarized using descriptive statistics.

For each additional infusion, the number of CD34+ cells, the number per kg, the final product volume, the total cells in the final product, the %CD34+, the CD34+ cells per mL and the final volume to be infused will be summarized using descriptive statistics.

8.2.16 Exposure

Duration of follow-up in months will be calculated as:

$$12 * (\text{date of final evaluation} - \text{date of infusion} + 1) / 365.25.$$

Duration of follow-up will be summarized using descriptive statistics. In addition, the total subject-years of follow-up will be presented.

8.3 Efficacy Evaluations

8.3.1 Primary Efficacy Endpoints

8.3.1.1 Response to OTL-101 Treatment at 6 Months

Response to OTL-101 treatment at 6 months post administration will be based on the following criteria:

- ADA activity in red blood cells: change from baseline >0 Units,
- Absolute CD3+ T-cell count $\geq 200/\text{mm}^3$, and
- Detectable gene-marked granulocytes by differential polymerase chain reaction (dPCR)/qPCR $\geq 1/10,000$ cells.

Subjects who meet all three criteria will be said to have mounted a response.

For any subjects with missing values at 6 months, the earliest assessments after month 6 will be used. In addition, if ADA activity at baseline is not available, any positive value will be considered as a positive response.

The number (%) of subjects mounting a response will be summarized and descriptively compared with the proportion from the UCLA “Fresh” study. In addition, the number (%) of subjects with a response to each of the individual criteria will be summarized.

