1.1.2.1 Hematopoietic Stem Cell Transplantation

Hematopoietic stem cell transplantation from allogeneic human leukocyte antigen (HLA)-compatible sibling donors is the treatment of choice for patients with SCID and other severe variants of primary immunodeficiency resulting in long-term survival of about 90% of patients and effective immune reconstitution ([Ferrua 2010](#)). However, as only 10–20% of patients are able to receive HSCT from an HLA-identical family member ([Stephan 1993, Antoine 2003](#)), transplants are often performed from mismatched family or matched unrelated donors (MUD). Despite improvements in pre-conditioning and post-transplant care, the use of less well matched HSCT is associated with reduced survival ([Gaspar 2009, Hassan 2012](#)) and delayed or suboptimal immune reconstitution in a significant fraction of surviving patients as a result of poor early engraftment or gradual decline in immune functions ([Railey 2009](#)). Complications such as Graft versus Host Disease (GvHD), autoimmune and inflammatory manifestations, persistent infections, and disease-related issues are often observed.

If a matched sibling/family donor is unavailable, most ADA-SCID patients are treated with ADA ERT. Enzyme replacement therapy leads to metabolic correction and clinical

improvement, but the immunological reconstitution is often incomplete and dysregulated (Hershfield 1987, Gaspar 2009, Sauer 2012) and therefore individuals remain at risk of severe infection. This approach does not represent a curative treatment modality and is not always available as a long-term option. Enzyme replacement therapy with polyethylene-glycol (PEG)-ADA was developed based on the concept that reduction of ADA substrate concentration in plasma results in lowering of intracellular concentrations of metabolites (Hershfield 1995). An intramuscular injection of PEG-ADA is administered weekly or bi-weekly, and is considered to be an excellent (although very expensive) short-term measure to stabilize children with ADA-SCID; however, prolonged use has associated risks as described in the IB.

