For subjects who have successfully received the OTL-101 product, PEG-ADA ERT use will be evaluated at the 1 Month follow-up visit (30 days post treatment ± 7 days) and discontinued at Day 30 (-3/+15) after the transplant. Hematologic reconstitution will be assessed at Day 42 (± 7 days), and in the event of no reconstitution the backup HSC sample will be administered, if the investigator believes this is in the subject's best interest. The subjects will then be seen at regular intervals to review their history, perform examinations and draw blood samples at Months 3, 6 and 9 (all ± 2 weeks) as well as Months 12, 18 and 24 (all ± 4 weeks). Any medically-indicated interventions, including the need to reinstate PEG-ADA ERT, will be assessed at all follow-up visits after Month 1. Hematopoietic reconstitution will be assessed again at the Month 6 visit and if there is still no evidence of cellular recovery, the subject will be given ERT and/or HSCT, if available and deemed appropriate by the Investigator. After the Month 24 visit, the subjects will have completed the study and may enter a long term registry.

This study will include three statistical analyses:

1. The first analysis will compare the success/failure data 6-months post OTL-101 infusion between fresh and cryopreserved OTL-101 formulations. The success/failure of OTL-101 will be defined by the three criteria listed in the primary objectives ([Section 2.2.1](#)). This data will be compared with available data from one of the ongoing Phase I/II studies using the OTL-101 fresh formulation. This will support the CMC comparability data between OTL-101 cryopreserved and fresh formulations. Secondary and exploratory endpoints will also be described.
2. The second analysis will determine the 12 month overall survival and event free survival for all subjects. Secondary and exploratory endpoints, as well as baseline characteristics, subject disposition, and safety data will also be described.
3. The third and final analysis will be performed to determine the overall survival and event free survival for all subjects 24 months post OTL-101 infusion. Secondary and exploratory endpoints, as well as baseline characteristics, subject disposition, safety and Busulfan pharmacokinetic (PK) data will also be described.

Efficacy analyses will be primarily descriptive in nature.

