All subjects included in the study will receive PEG-ADA (Adagen®) prior to OTL-101 infusion, which will be continued until Day 30 (+/-3 days) post-transplant. If, at Day 30 (+/-3 days) post infusion of OTL-101, the subject is not suffering from active infections or other major medical problems, PEG-ADA administration will be discontinued.

2. Rules for re-starting ERT or plan allogenic HSCT (if available)

If, by 6 months after the OTL-101 infusion, there is no evidence of hematopoietic reconstitution following the infusion of the back up OTL-101 and rescue medication/treatment, subjects will require rescue PEG-ADA or allogenic HSCT if available. Positive evidence of hematopoietic reconstitution will require:

- a. RBC ADA >0 Units,
- b. absolute CD3+ T-cell counts $\geq 200/\text{mm}^3$, and
- c. peripheral blood samples positive for vector sequences by qPCR ($>1/10,000$ cells).

In addition, PEG-ADA may be re-started if the Investigator deems it in the best interests of the subject on clinical grounds, e.g. multiple, serious or unresponsive infections or sub-normal immune reconstitution. Once ERT has been re-started, the subject will remain in the study and will continue to be followed-up. If the subject fails to demonstrate hematopoietic reconstitution and has the possibility of receiving an allogeneic transplant, the subject should be withdrawn from the study in order to follow institute transplantation protocols.

Once re-started, PEG-ADA may be discontinued if all the following criteria are met: no active infection, PBMC ADA >6 Units, absolute CD3+ T-cell counts $\geq 200/\text{mm}^3$, and peripheral blood samples positive for vector sequences by qPCR.

Prophylaxis for Infections

Prophylactic antimicrobial agents will be used to provide coverage for *Pneumocystis jirovecii* pneumonia and mucosal yeast:

- *Pneumocystis jirovecii* prophylaxis (PJP): Trimethoprim/sulfamethoxazole (TMP/SMX), which will be stopped prior to CD34+ cell harvest and then resumed when ANC >500 . If, after Day 30, ANC is <500 , an alternative PJP prophylaxis regimen will be used. Suitable alternative PJP prophylactic medications include pentamidine (intravenous or aerosolized) or atovaquone. Dapsone should be used with caution,

because of its potential myelosuppressive effects. PJP prophylaxis can be discontinued when CD4 >200/ μ l ([Griffith2009](#)).

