9.3.1 Primary Efficacy Endpoints

The primary efficacy endpoints for this study include treatment success at 6 months post OTL-101 infusion, and overall survival and event-free survival at 12 months post OTL-101 infusion.

Treatment success at 6 months post OTL-101 infusion, will be performed in support of CMC assessing comparability between cryopreserved and fresh formulations. Evaluation of the success of therapy will be based on the following parameters and their thresholds:

- a) Erythrocyte ADA enzyme activity above baseline/pre-treatment level (>0 Units),
- b) Absolute CD3+ T-cell counts $\geq 200/\text{mm}^3$, and
- c) Peripheral blood samples positive for vector sequences by qPCR($\geq 1/10,000$ cells).

Treatment will be deemed successful in subjects meeting all three above thresholds. These subjects will be designated as “responders”. Those subjects failing to meet at least one of the above thresholds will be considered to be “non-responders.”

Overall Survival is defined as the time-to death from the OTL-101 infusion if death occurred, or to the date of the last evaluation if death did not occur. If no death occurred, the subject’s data will be considered censored at the last evaluation.

Event Free Survival is defined as the time-to event from the OTL-101 infusion if an event occurred, or to the date of the last evaluation without an event if no event occurred. If no event occurred, the subject’s data will be considered censored at the last evaluation. Event is defined as any of the following:

- Death
- Returning to PEG-ADA ERT
- Need of rescue HSCT

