8.3.1.3 Event Free Survival at 12 Months

Event-free survival will be evaluated using the time in months from transplant to either the first event or their last evaluation calculated as:

$$12 * (\text{date of event/last evaluation} - \text{date of transplant}) / 365.25.$$

For the purpose of this analysis, the events of interest are:

- death;
- reinstitution of PEG-ADA ERT;
- requirement for a second transplant.

Event-free survival will be summarized in the same way as overall survival described in Section 8.3.1.2.

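### The 6-month responder rule ignores PEG-ADA status, so a subject who has restarted PEG-ADA can be counted as a success in the fresh-versus-cryopreserved comparison

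*SAP*

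**What the plan says.** **Responder rule.** SAP 8.3.1.1 sets three thresholds at 6 months: a rise in red-cell ADA over baseline, CD3+ of at least 200/mm³, and gene marking of at least 1 in 10,000 cells. It then states "Subjects who meet all three criteria will be said to have mounted a response". Protocol 9.3.1 agrees: "Treatment will be deemed successful in subjects meeting all three above thresholds". Neither mentions PEG-ADA. The rule for missing Month 6 data is "For any subjects with missing values at 6 months, the earliest assessments after month 6 will be used", and nothing covers values taken after a restart.

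**Restarting PEG-ADA.** Protocol 3.1 says "Any medically-indicated interventions, including the need to reinstate PEG-ADA ERT, will be assessed at all follow-up visits after Month 1", which includes Month 3. Protocol 6.2.1.1 adds to its 6-month laboratory rule that "PEG-ADA may be re-started if the Investigator deems it in the best interests of the subject on clinical grounds", and gives sub-normal immune reconstitution among its examples. It continues: "Once ERT has been re-started, the subject will remain in the study and will continue to be followed-up".

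**EFS.** SAP 8.3.1.3 lists "reinstitution of PEG-ADA ERT" as an event.

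**Timing and population.** SAP 7.1 puts every treated subject in the efficacy population. Under SAP 6 the first analysis, with at least 5 subjects at 6 months, compares response with the UCLA fresh-formulation study. EFS is evaluated at the second analysis. The PEG-ADA summary in SAP 8.3.3.1 is time to withdrawal, with no summary of restarts.

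**The concern.** The responder rate carries the clinical side of the fresh-versus-cryopreserved comparison, and Protocol 2.1 presents its components as predictors of EFS. A reader will take a responder to be someone whose own corrected cells are doing the work. As written, a child who restarted PEG-ADA at Month 3 because reconstitution was poor, and who passes the three tests at Month 6, is reported as a treatment success.

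The component most open to this is the CD3 count. Protocol 1.1.2.1 says "Enzyme replacement therapy leads to metabolic correction", with immune recovery that is often incomplete, so a CD3 count taken on PEG-ADA cannot be credited to OTL-101 alone. The first analysis is where this matters most, because the response comparison is made there before EFS, the endpoint that would register the restart, is evaluated.

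**Working it through.** **1. Can the case arise under the text?** Set side by side:

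- Restart before Month 6 is possible (Protocol 3.1 and 6.2.1.1).
- The subject stays in the study (Protocol 6.2.1.1) and in the efficacy population (SAP 7.1), and so reaches the Month 6 assessment.
- Scoring uses laboratory values only (SAP 8.3.1.1, Protocol 9.3.1).
- Passing the thresholds is compatible with being on PEG-ADA. Protocol 6.2.1.1 lists absence of active infection and PBMC ADA above 6 Units, besides CD3 and vector positivity, before a restarted course may end. The CD3 threshold of 200 also lies below the 300 cells/µL that Protocol 4.1 accepts as evidence of severe deficiency before treatment.
- Because a missing Month 6 value is replaced by a later one, a restart after Month 6 can also precede the value used.

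Nothing in either document prevents the case.

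**2. The plan's own precision figure.** Protocol 9.4 gives a half-width of 15% for 100% success at N=10 (exact binomial, two-sided 95%). For n/n the exact lower limit is 0.025^(1/n). With n=10 this is 0.6915, and the half-width is (1 − 0.6915)/2 = 15.4%. The stated figure is reproduced.

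**3. Effect of restarters.** Assume all subjects pass the three laboratory criteria and k of them restarted PEG-ADA before the assessment used. Exact limits for x/n are the 2.5% quantile of Beta(x, n−x+1) and the 97.5% quantile of Beta(x+1, n−x).

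| n | k | As written | Restart counted as non-response |
|---|---|---|---|
| 10 | 1 | 10/10 (69.2–100%) | 9/10 (55.5–99.7%) |
| 10 | 2 | 10/10 (69.2–100%) | 8/10 (44.4–97.5%) |
| 10 | 3 | 10/10 (69.2–100%) | 7/10 (34.8–93.3%) |
| 5 | 1 | 5/5 (47.8–100%) | 4/5 (28.4–99.5%) |

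Each such subject is worth 1/10 = 10 points at n=10 and 1/5 = 20 points at n=5. The intervals are illustrative: the plan specifies exact intervals for survival and EFS, but only number, percentage and a descriptive comparison for response.

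**4. How likely is a restarter?** No pre-Month-6 rate is given. Protocol 1.3.3 reports no restarts among 18 UCLA subjects, and one restart in the UK study with EFS of 93.3%, which fits 14/15. Together that is 1/33 = 3.0% over all follow-up, timing not stated. The chance of at least one restarter is 1 − (1 − p)^n, taking subjects as independent:

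| p | n=10 | n=5 |
|---|---|---|
| 1/33 | 26% | 14% |
| 5% (assumed) | 40% | 23% |
| 10% (assumed) | 65% | 41% |
| 20% (assumed) | 89% | 67% |

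For each assumed rate these are upper bounds on the chance of a miscounted subject, since not every restarter would pass all three criteria.

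**5. What if the protocol definition itself were changed?** Protocol 3.6.1 halts enrolment or treatment at three non-responders and withdraws non-responders. With k=3 the halting rule would be met under a changed definition but not as written. The remedy must therefore stay outside that definition.

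**The case against.** PEG-ADA alone is not shown to produce a responder. All three criteria must be met. Gene marking measures vector-bearing cells, and red-cell ADA must rise above a baseline taken before infusion, when subjects are already receiving PEG-ADA (Protocol 5.1.3 and 6.2.1.1). Protocol 6.2.1.1 also uses CD3 and vector positivity in subjects on restarted PEG-ADA, so it treats those values as informative there. This stands, and it limits the plausible confounding mainly to CD3.

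A reader might infer that the two primary endpoints contradict each other. The documents do not support that. One is a laboratory measure at 6 months, the other a clinical course to 12 months, and a restart for infection can occur in a subject with genuine engraftment. They may properly differ. The gap is the missing scoring rule.

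The restart is also not hidden. PEG-ADA use is recorded at each follow-up visit, each criterion is reported separately, SAP 8.4.2 plans a listing of concomitant medication, and EFS will register the event. With ten subjects and descriptive analysis, a careful reader could find it. But no planned table links restarts to response, and the headline comparison at the first analysis would not reflect them.

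Finally, redefining response in Protocol 9.3.1 would do harm. It would pull restarters into the withdrawal and halting rules, conflict with keeping them in the study, and give those withdrawn alive before 12 months an unknown survival status under SAP 8.3.1.2. This is right, and it shapes the fix.

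**Conclusion.** The point holds as a missing analysis rule. As written, a subject who restarted PEG-ADA before the assessment used can be counted as a responder in the fresh-versus-cryopreserved comparison. If that happens once, the reported rate is 10/10 where counting the restart as non-response would give 9/10, or 5/5 where it would give 4/5.

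This rests on two conditions: a restart before the assessment used, and a pass on all three criteria. A reader might infer that the responder rate is inflated. The documents show only that it could be, since they give no pre-Month-6 restart rate. With 0/18 restarts at UCLA at the cited data cut, the gap could raise only the cryopreserved rate on those data, though a later cut may differ.

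The analysis is descriptive and no error rate or power figure depends on this, so the matter is one of interpretation. It should be settled before the first analysis.

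**What to change.** Add to SAP 8.3.1.1, for analysis only:

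- In the fresh-versus-cryopreserved comparison, a subject who resumed PEG-ADA, had rescue HSCT or died before the assessment used is counted as a non-responder.
- The laboratory-only response, as now defined, is reported alongside.
- PEG-ADA restarts are listed at the first analysis, with dates relative to the assessment used.
- The same rule is applied to the UCLA fresh data.
- The rule does not alter the laboratory definition used for withdrawal and for the halting rule in Protocol 3.6.1.

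Separately, the sponsor should reconcile Protocol 6.2.1.1, under which a subject stays in the study after a restart, with Protocol 3.6.1, Protocol 5.1.7 (Month 6) and SAP 5.1, under which non-responders are withdrawn. No clinical rule is proposed here.

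The cost is a short SAP paragraph, one extra table and a possibly slightly lower responder rate. PEG-ADA use is already collected at the follow-up visits of this study. Whether the fresh data hold restart dates in the same form needs checking.
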